16.6 Inclusion of Women and Minorities

16.61 This study will be available to all eligible patients, regardless of race, gender, or ethnic origin.

16.62 There is no information currently available regarding differential effects of this regimen in subsets defined by race, or ethnicity, and there is no reason to expect such differences to exist. Therefore, although the planned analysis will, as always, look for differences in treatment effect based on racial, the sample size is not increased in order to provide additional power for subset analyses.

The diagnosis is more common in men, as the male:female ratio is approximately 2:1 (Weisenburger, Savage et al. 2011)

16.63 The geographical region served by MCCC has a population which includes approximately 3% minorities. Based on prior MCCC studies involving similar disease sites, we expect about 3-5% of patients will be classified as minorities by race and about 30% of patients will be women. Expected sizes of racial by gender subsets are shown in the following table:

Accrual Estimates by Gender/Ethnicity/Race

Ethnic Category	Sex/Gender			
	Females	Males	Unknown	Total
Hispanic or Latino	0	1	0	1
Not Hispanic or Latino	13	25	0	38
Ethnic Category: Total of all subjects	13	26	0	39
Racial Category				
American Indian or Alaskan Native	0	0	0	0
Asian	0	0	0	0
Black or African American	1	1	0	2
Native Hawaiian or other Pacific Islander	0	0	0	0
White	12	25	0	37
Racial Category: Total of all subjects	13	26	0	39

Ethnic Categories: **Hispanic or Latino** – a person of Cuban, Mexican, Puerto Rico, South or Central American, or other Spanish culture or origin, regardless of race. The term “Spanish origin” can also be used in addition to “Hispanic or Latino.”

Not Hispanic or Latino

Racial
Categories:

American Indian or Alaskan Native – a person having origins in any of the original peoples of North, Central, or South America, and who maintains tribal affiliations or community attachment.

Asian – a person having origins in any of the original peoples of the Far East, Southeast Asia, or the Indian subcontinent including, for example, Cambodia, China, India, Japan, Korea, Malaysia, Pakistan, the Philippine Islands, Thailand, and Vietnam. (Note: Individuals from the Philippine Islands have been recorded as Pacific Islanders in previous data collection strategies.)

Black or African American – a person having origins in any of the black racial groups of Africa. Terms such as “Haitian” or “Negro” can be used in addition to “Black or African American.”

Native Hawaiian or other Pacific Islander – a person having origins in any of the original peoples of Hawaii, Guam, Samoa, or other Pacific Islands.

White – a person having origins in any of the original peoples of Europe, the Middle East, or North Africa.

17.0 Pathology Considerations/Tissue Biospecimens

17.1 Summary Table of Research Tissue Specimens to be Collected for this Protocol

Correlative Study (Section for more information)	Mandatory or Optional	Type of Tissue to Collect	Block, Slides, Core, etc. (# of each to submit)	Baseline	At Progression	Specific Details for submission
Pathology review – confirm diagnosis	Mandatory for diagnoses made at non- Mayo sites	H & E, stained slides	All H&E stained diagnostic slides	X		17.2
Correlative studies	Mandatory	Paraffin sections	Tissue block (preferred) or unstained slides (10 slides), 4-5 microns each	X	X ¹	17.3

1. Samples are required, however there is no protocol violation if sample is not obtained.

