17.2 Diagnostic Slides from Original and /or Recurrent Tissue

- 17.21 Central pathology review is not required as long as the tissue diagnosis of lymphoma was confirmed by a Mayo pathologist. If the tissue diagnosis is not confirmed by a Mayo pathologist, the slides will need to be reviewed to confirm the diagnosis. Completion of central pathology review is not required prior to registration; however materials for central review must be reviewed within 42 days after registration.
- 17.22 Central pathology review will be conducted as needed for confirmation of diagnosis by [name] and colleagues at Mayo Clinic Rochester if the initial tissue biopsy was not performed and evaluated at Mayo Clinic.
- 17.23 Required materials:
- Lymphoma Pathology Reporting Form (Complete Section I only)
 - Tissue Submission Form
 - Tumor tissue pathology report

- Paraffin block containing tumor tissue from the most recent tumor tissue biopsy is preferred, not bone marrow or peripheral blood. If the institution is unwilling to release a block, 18 unstained, charged slides cut at 4-5 microns should be submitted. Slides should be placed in appropriate slide container.
- All tumor tissue diagnostic H&E stained slides
- Tumor tissue immunochemistry or immunophenotyping by flow cytometry report (if available)

After central review is completed, the pathologist will return all diagnostic slides to the submitting outside institution. In addition, the pathologist will also forward the completed Lymphoma Pathology Reporting Form and accompanying reports to the study QAS for scanning and data entry purposes to the following:

QAS for MC1681

Mayo Clinic

[REDACTED]
[REDACTED]
Rochester, MN [REDACTED]
Phone: [REDACTED]

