17.32 Paraffin Embedded Tissue

17.321 Paraffin embedded tissue block will be used to generate tumor derived genomic DNA for the correlative studies as described in section 17.4.

17.322 If tissue block is not available, then Ten (10) 4-5 micron paraffin embedded tissue slides will be collected for DNA isolation and sequencing.

17.323 Eight (8) 4-5 micron paraffin embedded tissue slides will be collected for staining cell specific markers for T cells, T cell subsets, tumors and PD-1, PD-L1, etc. other related co-stimulatory or inhibitory markers.

17.324 Shipping

Specimens need to be labeled with patient initials and study ID number, sex, age and specific diagnosis for the trial enrollment.

Ship specimens via Priority Overnight service on Monday – Thursday Preferred (Friday only if you must) directly to:

Predolin Biobank Attn: [REDACTED]

[REDACTED]
[REDACTED]
Rochester, MN [REDACTED]

Please email [REDACTED] or call [REDACTED] to notify the laboratory when specimens are being shipped. The message should include the study name, sample type, Fed Ex air bill tracking number, contact name and telephone number.

Shipping costs will be covered by the study.

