17.4 Background and Methodology

Background: Accumulating evidence has shown that clinical responses to checkpoint inhibitor is likely associated with tumor PD-L1 overexpression as well as tumor exomic mutation burden. Therefore, we plan to test the spectrum of tumor mutations using WES/targeted sequencing as well as measure tumor PD-L1 and other marker staining with immunohistochemistry analysis

- 17.41 **Sequencing:** Genomic DNA will be extracted from formalin-fixed, paraffin-embedded tissue blocks. H&E-stained sections from each case will be reviewed by an expert hematopathologist and representative blocks with at least 30% tumor cells will be selected. 10 x 5-micron sections will be cut from blocks in the Mayo Clinic Pathology Research Core (based on tissue area of 25 mm²). DNA will be extracted in the Mayo Clinic Biospecimens Accessioning and Processing Core using the Qiagen FFPE DNA extraction kit. DNA quantitation will be performed using a Qubit fluorometer prior to sequencing.
- 17.42 **Immunohistochemistry (IHC):** Expression of PD-L1 has been demonstrated to associate with clinical response of cancer patients treated with nivolumab. It is also established that CD8⁺ cytotoxic T cell response is critical to mediate anti-tumor immunity. Therefore, multiple markers including T cell, tumor cells, as well as related co-stimulatory and inhibitory markers will be stained to identify if there is any association of expression of these markers with clinical response. Serial 5- μ m paraffin-embedded sections will be used for IHC. The tissue will be deparaffinized with three changes of xylene and cleared through graded series of ethanol. Endogenous peroxidase will be quenched by incubation in 50% methanol/H₂O₂ and after rinsing with tap water; all sections will be pretreated for 30 minutes with 50 mmol/L EDTA using a steamer and cooled for additional 5 minutes. All staining will be done automatically on DAKO Autostainer using the following antibodies to CD11c (Leica Microsystems 5D11), CD14 (Cell Marque EPR 3653), CD163 (DAKO 1F8), CD68 (DAKO PG-M1), CXCL13 (R&D Systems 53610), FOXP3 (Abcam 236AE/7), CD3 (R&D Systems), PD-L1 (405.9A11), PD-L2 (366C.9E5) and PD-1 (Abcam NAT). The sections will be viewed with an Olympus BXFA51 microscope and pictures taken with an Olympus DP71 camera.

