**** PLEASE AVOID DRAWING OR SENDING SPECIMENS ON FRIDAYS AND HOLIDAYS****

Kit Contents:

- Small Styrofoam box and cardboard mailing sleeve
- Patient Information Form
- FedEx Airbill with pre-printed return address
- One 6ml ACD (yellow) collection tube
- One 10ml EDTA (purple) collection tube
- One 10ml Red Top collection tube
- Absorbent tube holder
- Zip lock specimen bag

Packing and Shipping Instructions:

1. Collect the following specimens:
 - Bone marrow – 6ml in one (1) ACD tube (Collected at Baseline only)

 - Peripheral blood – Draw:
 - 10ml in one (4) EDTA tube
 - 10ml in one (1) Red top tube

2. All specimens are to be clearly labeled with the protocol number MC1681, the patient's initials (last, first, middle), study patient ID (if available), type of sample (bone marrow or peripheral blood), and date of collection.
3. Place the tubes in the absorbent holder and seal in the zip lock specimen bag.
4. Place the filled specimen bag in the Styrofoam container.
5. Loosely pack with paper toweling.
6. Place the Styrofoam container and the Patient Information form within the cardboard mailing sleeve.
7. Prepare the package for shipping, applying packing tape as needed. Adhere the Fed Ex Airbill to the exterior of the box. Ship specimens via priority overnight delivery (next day delivery by 10am) the same day collected.
8. Notify Federal Express for pick-up and/or leave package at the designated FedEx drop-off location.

Please email [REDACTED] or call [REDACTED] to notify the laboratory when samples are being shipped. Indicate the protocol number MC1681, the Fed Ex tracking number, name and phone number of the contact person. The samples in prepared kits should be shipped to the following:

Predolin Biobank Attn: [REDACTED]
[REDACTED]
Rochester, MN [REDACTED]

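### The specimen instructions contradict each other: 10 against 18 unstained slides when no block is sent, and one against four EDTA tubes per blood kit

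*Combined protocol and SAP*

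**What the plan says.** **Tissue.** The correlative row of the section 17.1 table is mandatory, is marked for baseline and progression, and asks for "Tissue block (preferred) or unstained slides (10 slides), 4-5 microns each". It points to section 17.3 for details. There, 17.322 reads "If tissue block is not available, then Ten (10) 4-5 micron paraffin embedded tissue slides will be collected for DNA isolation and sequencing", and 17.323 reads "Eight (8) 4-5 micron paraffin embedded tissue slides will be collected for staining cell specific markers for T cells", going on to T-cell subsets, tumor, PD-1, PD-L1 and related markers. Section 17.23, which lists the materials for central pathology review, says that if a block is not released, "18 unstained, charged slides cut at 4-5 microns should be submitted". Section 17.21 waives that review where a Mayo pathologist has confirmed the diagnosis.

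**Blood.** The section 14.1 table requires four 10 mL EDTA tubes and one 10 mL red-top tube on Day 1 of Cycles 1 to 4, at the end of Cycle 12, at end of treatment and at progression. The Appendix III kit list contains "One 10ml EDTA (purple) collection tube" and one red-top tube. The draw line in the same appendix has the word for one next to the numeral 4 for the EDTA tubes. Section 14.33 states that a kit holds all the tubes required.

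**The concern.** These are working collection figures, and a site may consult only one of them. A coordinator who takes the 17.1 table at its word and has no block sends ten slides, which is exactly what 17.322 allots to sequencing. A coordinator who opens the kit finds one EDTA tube where 14.1 wants four.

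The aim most exposed is goal 2.33, which relates PD-L1, PD-1 and PD-L2 expression, and soluble PD-L1 in plasma, to efficacy. Its tissue half needs the staining slides. Its plasma half draws on EDTA blood, because section 14.21 takes plasma and blood DNA from the EDTA tube. A pre-dose draw cannot be repeated once the dose is given. With at most 39 patients planned (section 16.22), each incomplete set is a noticeable loss to an exploratory comparison.

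Shortfalls may also go unremarked. Footnotes to both tables say that a missing progression sample is not a violation, and the 14.1 footnote says the same of the end-of-treatment blood.

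**Working it through.** **Slides when no block is sent**

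| Source | Slides |
|---|---|
| 17.322, DNA and sequencing | 10 |
| 17.323, staining | 8 |
| Sum | 10 + 8 = 18 |
| 17.23, central-review materials | 18 |
| 17.1 table, correlative row | 10 |

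1. The sum of the two uses reproduces the 18 in section 17.23, so 18 appears to be the intended total and the 17.1 table is the figure out of line.
2. Shortfall under the 17.1 table: 18 − 10 = 8 slides, and 8/18 = 44%.
3. If DNA takes its share first, 10 − 10 = 0 slides remain for staining. If staining is served first, 10 − 8 = 2 remain for DNA. Ten slides cannot serve both.
4. Section 17.41 supports the DNA figure: "10 x 5-micron sections will be cut from blocks in the Mayo Clinic Pathology Research Core".
5. Does 18 cover every assay? Section 17.42 names ten antibodies (CD11c, CD14, CD163, CD68, CXCL13, FOXP3, CD3, PD-L1, PD-L2, PD-1) against eight staining slides, and 17.43 adds FISH. The documents do not say how many antibodies share a slide. Assuming one per slide, the total would be 10 + 10 = 20, or 21 with one slide for FISH. If antibodies can share slides and FISH also fits within the eight, 18 is enough. The documented figure is therefore 18, with 18 to 21 as the range across these assumptions.

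**EDTA blood**

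1. Section 14.1: 4 × 10 mL = 40 mL per draw.
2. Appendix III kit list: 1 × 10 mL = 10 mL per draw.
3. Shortfall: 40 − 10 = 30 mL, and 30/40 = 75%.
4. Over the four pre-treatment draws of Cycles 1 to 4: 4 × 40 = 160 mL specified against 4 × 10 = 40 mL, if the kit is used as packed each time.
5. Red-top serum: 10 mL in 14.1 and 10 mL in the kit, so there is no gap. The 30-cytokine panel in 14.412 is a serum assay and keeps its material.
6. Peripheral blood cells for flow cytometry: 14.21 marks flow cytometry only for the ACD tube, which 14.1 collects at baseline as tumor or marrow. The tube for blood mononuclear cells is not named. EDTA is the likely source, since the red-top tube is listed as yielding serum only, but that is an inference.

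**The case against.** The best answer is that the right figures are already in the protocol. The 17.1 row sends the reader to 17.3, where ten and eight are both listed; 17.23 states 18 outright; 14.1 states four tubes, and the Appendix III draw line carries a 4. The tissue gap is also narrow. It arises only without a block, and a block is preferred. Section 17.22 triggers central review when the initial biopsy was not performed and evaluated at Mayo, and 17.23 then asks for 18. What remains is mainly progression samples, and baseline cases already confirmed by a Mayo pathologist where the block is withheld. The kit check in 6.9c does not apply to Rochester.

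All of that stands, and it makes this a matter of conflicting instructions rather than a uniform under-request. It does not remove the conflict: the row that governs correlative tissue at both timepoints says 10, and the kit list cannot meet 14.1.

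Three stronger readings are tempting and not supported.

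- **That about 22 slides are required.** This needs one antibody per slide plus separate FISH and H&E slides, giving 10 + 10 + 1 + 1. The documents state none of this, and 17.41 uses H&E review to choose blocks, which is not the no-block case.
- **That the on-treatment blood assays lose their material.** Serum is intact and 10 mL of EDTA blood would remain. Section 14.4 gives no assay volume, so nothing shows that 10 mL is inadequate; four tubes is the 14.1 collection requirement.
- **That a particular assay must come first when tissue is short.** The documents set no order, and choosing one is a scientific preference.

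**Conclusion.** The point holds as two internal contradictions in operative collection instructions: 10 against 18 slides per sample sent without a block (8 short, 44%), and 10 mL against 40 mL of EDTA blood per draw if the kit is used as listed (30 mL short, 75%). The slide figure assumes that the quantities in 17.322 and 17.323 are both wanted when no block is sent, as the matching total in 17.23 indicates. The blood figure assumes that a site draws only into the tubes supplied.

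How many patients are affected cannot be estimated, because the documents do not say how often a block will be withheld or how patients divide among the three sites. The consequence is confined to the exploratory correlatives, chiefly goal 2.33. The primary response analysis and the 35-patient decision rule are untouched. The correction is worth making because it is specific and cheap, and because missed pre-dose blood cannot be recovered.

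**What to change.** - **Section 17.1 table, correlative row:** ask for a block or 18 unstained slides at both baseline and progression, so that it agrees with 17.322 plus 17.323 and with 17.23.
- **Sections 17.323, 17.42 and 17.43:** have the laboratory confirm whether ten antibodies and FISH fit on eight staining slides. If they do not, raise the count in 17.323, the 17.1 table and 17.23 together.
- **Appendix III:** list four 10 mL EDTA tubes in the kit, and make the draw line say four in both word and numeral, matching 14.1 and making the statement in 14.33 true.

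The cost is wording, three more tubes per kit, and eight more sections for each sample sent without a block (up to 2 × 8 = 16 for a patient sampled at both timepoints). The institution holding the block has to cut those sections. No blood is drawn beyond what 14.1 already specifies.

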17.2 Diagnostic Slides from Original and /or Recurrent Tissue

- 17.21 Central pathology review is not required as long as the tissue diagnosis of lymphoma was confirmed by a Mayo pathologist. If the tissue diagnosis is not confirmed by a Mayo pathologist, the slides will need to be reviewed to confirm the diagnosis. Completion of central pathology review is not required prior to registration; however materials for central review must be reviewed within 42 days after registration.
- 17.22 Central pathology review will be conducted as needed for confirmation of diagnosis by [name] and colleagues at Mayo Clinic Rochester if the initial tissue biopsy was not performed and evaluated at Mayo Clinic.
- 17.23 Required materials:
- Lymphoma Pathology Reporting Form (Complete Section I only)
 - Tissue Submission Form
 - Tumor tissue pathology report

- Paraffin block containing tumor tissue from the most recent tumor tissue biopsy is preferred, not bone marrow or peripheral blood. If the institution is unwilling to release a block, 18 unstained, charged slides cut at 4-5 microns should be submitted. Slides should be placed in appropriate slide container.
- All tumor tissue diagnostic H&E stained slides
- Tumor tissue immunochemistry or immunophenotyping by flow cytometry report (if available)

After central review is completed, the pathologist will return all diagnostic slides to the submitting outside institution. In addition, the pathologist will also forward the completed Lymphoma Pathology Reporting Form and accompanying reports to the study QAS for scanning and data entry purposes to the following:

QAS for MC1681

Mayo Clinic

[REDACTED]
[REDACTED]
Rochester, MN [REDACTED]
Phone: [REDACTED]

17.3 Correlative Tissue Collection

17.31 Tissue Kits will not be provided for this protocol.

17.32 Paraffin Embedded Tissue

17.321 Paraffin embedded tissue block will be used to generate tumor derived genomic DNA for the correlative studies as described in section 17.4.

17.322 If tissue block is not available, then Ten (10) 4-5 micron paraffin embedded tissue slides will be collected for DNA isolation and sequencing.

17.323 Eight (8) 4-5 micron paraffin embedded tissue slides will be collected for staining cell specific markers for T cells, T cell subsets, tumors and PD-1, PD-L1, etc. other related co-stimulatory or inhibitory markers.

17.324 Shipping

Specimens need to be labeled with patient initials and study ID number, sex, age and specific diagnosis for the trial enrollment.

Ship specimens via Priority Overnight service on Monday – Thursday Preferred (Friday only if you must) directly to:

Predolin Biobank Attn: [REDACTED]

[REDACTED]
[REDACTED]
Rochester, MN [REDACTED]

Please email [REDACTED] or call [REDACTED] to notify the laboratory when specimens are being shipped. The message should include the study name, sample type, Fed Ex air bill tracking number, contact name and telephone number.

Shipping costs will be covered by the study.

17.4 Background and Methodology

Background: Accumulating evidence has shown that clinical responses to checkpoint inhibitor is likely associated with tumor PD-L1 overexpression as well as tumor exomic mutation burden. Therefore, we plan to test the spectrum of tumor mutations using WES/targeted sequencing as well as measure tumor PD-L1 and other marker staining with immunohistochemistry analysis

- 17.41 **Sequencing:** Genomic DNA will be extracted from formalin-fixed, paraffin-embedded tissue blocks. H&E-stained sections from each case will be reviewed by an expert hematopathologist and representative blocks with at least 30% tumor cells will be selected. 10 x 5-micron sections will be cut from blocks in the Mayo Clinic Pathology Research Core (based on tissue area of 25 mm²). DNA will be extracted in the Mayo Clinic Biospecimens Accessioning and Processing Core using the Qiagen FFPE DNA extraction kit. DNA quantitation will be performed using a Qubit fluorometer prior to sequencing.
- 17.42 **Immunohistochemistry (IHC):** Expression of PD-L1 has been demonstrated to associate with clinical response of cancer patients treated with nivolumab. It is also established that CD8⁺ cytotoxic T cell response is critical to mediate anti-tumor immunity. Therefore, multiple markers including T cell, tumor cells, as well as related co-stimulatory and inhibitory markers will be stained to identify if there is any association of expression of these markers with clinical response. Serial 5- μ m paraffin-embedded sections will be used for IHC. The tissue will be deparaffinized with three changes of xylene and cleared through graded series of ethanol. Endogenous peroxidase will be quenched by incubation in 50% methanol/H₂O₂ and after rinsing with tap water; all sections will be pretreated for 30 minutes with 50 mmol/L EDTA using a steamer and cooled for additional 5 minutes. All staining will be done automatically on DAKO Autostainer using the following antibodies to CD11c (Leica Microsystems 5D11), CD14 (Cell Marque EPR 3653), CD163 (DAKO 1F8), CD68 (DAKO PG-M1), CXCL13 (R&D Systems 53610), FOXP3 (Abcam 236AE/7), CD3 (R&D Systems), PD-L1 (405.9A11), PD-L2 (366C.9E5) and PD-1 (Abcam NAT). The sections will be viewed with an Olympus BXFA51 microscope and pictures taken with an Olympus DP71 camera.
- 17.43 **Fluorescence in situ hybridization (FISH):** PD-L1 overexpression is commonly due to genetic mutations of the PD-L1 locus. FISH will therefore be performed to assess copy number at chromosome 9p24.1. The bacterial artificial chromosome probes (CHORI; www.chori.org) RP11-599H2O, which maps to 9p24.1 and includes CD274 (encoding PD-L1, labeled with Spectrum Orange), and RP11-635N21, which also maps to 9p24.1 and includes PDCD1LG2 (encoding PD-L2, labeled with Spectrum Green), will be cohybridized. A control centromeric probe, Spectrum Aqua-labeled CEP9 (Abbott Molecular) that maps to 9p11-q11, will be hybridized according to the manufacturer's recommendations. Nuclei with a target:control probe ratio of at least 3:1 will be classified as amplified, those with a probe ratio of more than 1:1 but less than 3:1 will be classified as relative copy gain, and those with a probe ratio of 1:1 but with more than two copies of each probe will be classified as polysomic for chromosome 9p.

